### **Literacy of Suicide Scale (LOSS) – Short Form (Q21)**

The LOSS consists of 12 statements assessing literacy of suicide. Participants are asked to rate each statement based on whether they think it is “True”, “False” or “Don’t know”. The statements reflect four domains of suicide literacy: Treatment/Prevention, Risk Factors, Signs, and Causes/Nature. Higher scores are reflective of greater suicide literacy. The 12 statements, their correct answer and corresponding domains are listed below:

Statement	Correct Answer	Domain
People who have thoughts about suicide should not tell others about it	F	Treatment/Prevention
Seeing a psychiatrist or psychologist can help prevent someone from suicide	T	Treatment/Prevention
Most people who suicide are psychotic	F	Risk Factors
Talking about suicide always increases the risk of suicide	F	Causes/Nature
A suicidal person will always be suicidal and entertain thoughts of suicide	F	Causes/Nature
Not all people who attempt suicide plan their attempt in advance	T	Signs
Very few people have thoughts about suicide	F	Causes/Nature
If assessed by a psychiatrist, everyone who kills themselves would be diagnosed as depressed	F	Causes/Nature
Men are more likely to die by suicide than women	T	Risk Factors
People who talk about suicide rarely kill themselves	F	Signs
People who want to attempt suicide can change their mind quickly	T	Signs
There is a strong relationship between alcoholism and suicide	T	Risk Factors

### **Patient Health Questionnaire Depression Scale (PHQ-8) (Q22)**

Depressive symptoms will be measured by the PHQ-8. This scale consists of 8 items that cover the DSM-IV symptoms of depression. These items are rated on a 4-point scale (0: not at all; 1: several days; 2: more than half the days; 3: nearly every day) to indicate how often the participant has been experiencing each symptom during the past two weeks. Higher scores indicate the presence of more depressive symptoms.

### **UCLA 3 Item Loneliness Scale (Q23)**

Loneliness will be measured by the **UCLA 3 Item Loneliness Scale**. This scale comprises three questions that measure three dimensions of loneliness: relational connectedness, social connectedness and self-perceived isolation. The questions are: ‘How often do you feel that you lack companionship?’, ‘how often do you feel left out?’, and ‘how often do you feel isolated from others?’. These items are rated on a 3-point scale (1: hardly ever; 2: some of the time; 3: often), with a total score range from 3 -9. Higher total scores indicate a greater degree of loneliness, with an option to categorise scores 3 – 5 as “not lonely” and score 6 – 9 as “lonely”.

### **Confidence Supporting Peers Scale (Q24-26)**

Four items will be used to assess respondents’ confidence and willingness to support a friend or peer who is experiencing personal difficulties. Responses are on a 5-point scale from 1 (not at all) to 5 (extremely) or a Yes/No/Don’t know scale. These items have been drawn from the evaluation of the Silence is Deadly intervention.

### **Short Warwick-Edinburgh Mental Wellbeing Scale (SWEMWBS) (Q27)**

The SWEMWBS was used to assess mental wellbeing. Seven statements are positively worded with five response categories from ‘none of the time’ to ‘all of the time’. Participants

are asked to describe their experiences over the past two weeks. The scale is scored by first summing the score for each of the seven items and then transforming the total raw scores to metric scores using the SWEMWBS conversion table which [can be found here](#). Scores range from 7 to 35 and higher scores indicate a greater degree of positive mental well-being.

### 3.2 Data management

Trial participants:

All participants will be allocated a study identifier, which will contain the first three letters of their school's name and a randomly generated four-digit number. Participant data from the surveys will be stored with the study identifier only. The file linking the study identifier with participant details will be kept under strict security (password protected), with access to authorised personnel only. Data released for analyses will not contain identifying information. All data will be handled in accordance with the relevant privacy legislation. Data will be stored on a secure, password protected server provided by University of New South Wales, with only nominated research personnel having access. An expert data manager will be involved early in the establishment of the first site to ensure that all data is handled and stored in such a way that is consistent with relevant privacy legislation. No participant will be identifiable in any publications, with aggregate results reported in all publications.

Data retention:

Data will be stored in digital format on secure servers, provided by the University of New South Wales, for 5 years after publication (or 7 years after project completion). The data will only be accessible by the researchers, who require a staff identification number and password to access the server. Personal information will be accessed, used and stored in accordance with Commonwealth Privacy Laws and the NSW Health Records and Information Privacy Act 2002. No individuals will be personally identified in the reporting of the results.

### 3.3 Statistical methods

Linear mixed models will be used to test the effect of the intervention on continuous, scaled outcome measures between groups and are able to include participants with missing data without using biased techniques. These models will include fixed effects for intervention status (baseline/unexposed vs post intervention and follow-up occasions) and random effects for cluster (school) and for participants within schools. Binary and count outcomes will be evaluated using generalized extensions of the mixed models used for scaled variables. Analysis of program fidelity data will involve univariate analysis of quantitative data. Specifically, regression analysis will be used to assess whether pre to post change in program outcomes is moderated by fidelity to the program.

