## 1.2 Objectives

The primary aim of the YAM study is to determine whether there is a significant decrease in suicidal ideation severity across time (from immediate post-intervention and 3-month follow-up, compared to baseline) compared to a waitlist control group.

The study also aims to determine whether students receiving YAM compared to students receiving classes as usual (the waitlist control group), will have reported:

- a) Reduction in the rate of self-harm at 3-month follow-up;
- b) Increase in help-seeking intentions for suicide immediately post-intervention and 3-month follow-up;
- c) Increase in help-seeking behaviour for suicide immediately post-intervention and 3-month follow-up;
- d) Decrease in suicide stigma immediately post-intervention and 3-month follow-up;
- e) Increase in suicide literacy immediately post-intervention and 3-month follow-up;
- f) Decrease in depression symptoms immediately post-intervention and 3-month follow-up;
- g) Decrease in loneliness immediately post-intervention and 3-month follow-up;
- h) Increase in confidence supporting peers immediately post-intervention and 3-month follow-up;
- i) Increase in mental wellbeing immediately post-intervention and 3-month follow-up.

Process outcomes for the implementation of the YAM intervention in the ACT will also be evaluated; including:

- a) Number of schools contacted and signed on for participation in the YAM program;
- b) Number of Instructors and Helpers trained to deliver YAM;
- c) Number of schools that completed the YAM program;
- d) The extent to which the program was delivered as prescribed;

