### 1.5 Procedure

*Cluster A schools:*

Consenting schools will be randomly allocated to the intervention or waitlist arm via cluster randomisation. Students in Cluster A schools will complete a baseline survey before participating in the YAM program and immediate post survey after program completion, all occurring in Term 2, 2020. They will then complete a 3-month post survey in Term 3, 2020.

*Cluster B schools:*

Surveys will be administered at the same time for students in Cluster B schools, but instead of receiving the YAM program in Term 2, 2020, they will have classes as usual. These students will receive YAM in Term 4, 2020.

If there are schools receiving the YAM program in Term 3, 2020 we aim to invite them to participate in the study as additional data would be valuable. These schools would administer surveys at pre- and post-YAM only, within Term 3.

The survey will take approximately 30 minutes to complete. All data will be securely stored at the Black Dog Institute, UNSW, with access to the data restricted to trial personnel and investigators.

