## 2.7 Sample size

We estimate that 15 government schools and 18 Independent/Catholic schools will be eligible to participate. The specific numbers of schools, staff and students per site is as follows:

1. Government schools: 15 eligible schools and 2378 Year 9 students.
2. Non-government schools: 18 eligible schools and 2494 Year 9 students.

Given that school participation rates are estimated to range between 50-65% ( $19 \times 0.5 = 7.5$ ), and the proportion of students from participating schools returning consent forms will be approximately 20% ( $1189 / 0.2 = 238$ ), an initial sample size for the Cluster A & B schools is set at a conservative 119 students per Cluster.

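### Section 3.3 codes intervention status with baseline and unexposed rows on one level and names no survey-occasion effect; fitted as worded, much of any change shared by both arms would be credited to YAM

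*Protocol*

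**What the plan says.** Protocol 3.3 gives the purpose of the linear mixed models as "to test the effect of the intervention on continuous, scaled outcome measures between groups". It then names the terms: "These models will include fixed effects for intervention status (baseline/unexposed vs post intervention and follow-up occasions", together with "random effects for cluster (school) and for participants within schools". Binary and count outcomes get generalised versions of the same models. No effect of survey occasion, of arm, or of arm by occasion is named.

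The primary aim in 1.2 is a fall in suicidal ideation severity at the two later surveys, "compared to baseline) compared to a waitlist control group". Every hypothesis in 1.3 is likewise a comparison with control.

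On timing, 1.5 says: "Surveys will be administered at the same time for students in Cluster B schools". Of the same waitlist students it says: "These students will receive YAM in Term 4, 2020". Table 1 in 1.4 puts their 3-month survey in Term 3. They are therefore unexposed at all three surveys.

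**The concern.** The stated coding contrasts two kinds of row. One level holds baseline and unexposed rows; the other holds rows after YAM. Because Cluster B is never exposed before its last survey, this gives:

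| | Baseline | Immediate post | 3-month |
|---|---|---|---|
| Cluster A (YAM) | reference | YAM | YAM |
| Cluster B (waitlist) | reference | reference | reference |

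Cluster B students never change status, so they contribute nothing to the within-student part of the estimate. That part is simply Cluster A's change from its own baseline. Without an occasion term, nothing in the model absorbs change that happens in both arms between surveys.

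Such change is plausible. The surveys run from Term 2 into Term 3, the same questionnaire is repeated, and under 4.3 students in either arm who endorse risk items are referred to the school wellbeing team. A shared improvement would then look like a YAM benefit, and a shared worsening would hide one. Surveying the waitlist arm at the same times makes it possible to remove this change; the stated coding largely gives that up.

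**Working it through.** **Inputs from the protocol.** Three surveys per student in each arm (1.4); Cluster B unexposed throughout (1.5); random intercepts for school and participant (3.3); equal arms, "set at a conservative 119 students per Cluster" (2.7). The 119 reproduces: 2378 x 0.5 = 1189; 1189 x 0.2 = 237.8; 237.8 / 2 = 118.9. (The division sign printed in 2.7 must mean multiplication.) It is used here only to fix the arm sizes. The protocol states no figure for bias or error rate.

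**Assumptions.** The protocol gives no school ICC, no within-student correlation r (total, including the school part) and no expected shift. I take r from 0.1 to 0.9, ICC from 0 to 0.10, total variance 1, known variances and complete data. Layouts per arm are 4 schools of 30 students (120) and 7 schools of 17 (119). The true YAM effect is 0, and both arms shift by d at both later surveys.

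**Step 1: zero correlation.** With n students per arm, the YAM rows average d. The reference level has n rows from Cluster A (baseline) and 3n from Cluster B, which is 4n, of which 2n carry d; its mean is d/2. The expected coefficient is d - d/2 = 0.50d.

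**Step 2: with correlation.** The estimate is a weighted mean of a within-student part, which equals d, and a between-school part, which equals 0 because the arms have equal means. With m students per school and D = 1 + 2r + 3(m - 1)ICC, the weights are proportional to 1/(1 - r) and 1/D. The share of d credited to YAM is therefore

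share = D / (D + 1 - r).

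- ICC 0: share = (1 + 2r)/(2 + r), giving 0.571 (r 0.1), 0.800 (r 0.5) and 0.966 (r 0.9).
- ICC 0.02, r 0.6, m = 30: D = 2.2 + 1.74 = 3.94; share = 3.94/4.34 = 0.908.
- ICC 0.02, r 0.6, m = 17: D = 2.2 + 0.96 = 3.16; share = 3.16/3.56 = 0.888.
- ICC 0.10, r 0.9, m = 30: D = 2.8 + 8.7 = 11.5; share = 11.5/11.6 = 0.991.

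A generalised least squares calculation gives the same values. One pooled YAM coefficient and separate coefficients for the two later surveys give the same share when the shift is equal at both.

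**Step 3: relaxing the conditions.**

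- Unequal arms at zero correlation: share = (nA + nB)/(nA + 3nB). For 3 v 5 schools this is 8/18 = 0.44; for 2 v 6 it is 8/20 = 0.40. With 2 v 6, ICC 0 and r 0.1 it is 0.47.
- Shift d at the 3-month survey only: one pooled coefficient is 0.25d at zero correlation, 0.45d at ICC 0.02 and r 0.6 (4 x 30), and approaches 0.50d. With two coefficients at ICC 0.02 and r 0.6, they are -0.05d (immediate post) and 0.95d (3-month).

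**Step 4: with occasion effects.** The expected YAM coefficient is 0.000d at every ICC and r tried.

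**Step 5: precision** (4 x 30, ICC 0.02, r 0.6, YAM effect at one survey).

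- As worded: variance = 1/{(2n/3)[1/(1 - r) + 1/D]} + (1 - r)/(2n) = 1/{80 x (2.5 + 0.254)} + 0.4/240 = 0.00454 + 0.00167; SE 0.079.
- With occasion effects: variance = 1/{(n/3)/(1 - r) + (2n/3)/D} + (1 - r)/n = 1/(100 + 20.3) + 0.4/120 = 0.00831 + 0.00333; SE 0.108.
- Ratio 1.37; over the grid 1.27 to 1.41.

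**Step 6: false-positive rate as worded** (same setting). A nominal two-sided 5% test rejects 10% of the time at noncentrality 0.652, so d = 0.652 x 0.0788/0.908 = 0.057 SD; over the grid, 0.03 to 0.12 SD. At d = 0.1 SD the noncentrality is 0.908 x 0.1/0.0788 = 1.15 and rejection is about 21%; at d = 0.2 SD it is about 63%.

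**The case against.** The strongest objection is that 3.3 is an outline and its parenthesis is shorthand. The preceding sentence speaks of a test between groups, 1.2 and 1.3 set a comparison with control, and the term for fixed effects is plural. An arm-by-occasion model would fit all of this, and a statistical analysis plan, which is not at hand, may state it. This stands as far as it goes: the documents do not show that the biased model will be fitted. It does not remove the point, because 3.3 does not leave the coding open. It states one, and that coding does not estimate the aim in 1.2.

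A reader might infer that at least half of any shared change would always go to YAM. The calculation does not support that. Half is a floor only with equal arms and the same shift at both later surveys, and schools are randomised, so student numbers need not balance (Step 3).

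A reader might also list regression to the mean among the shared changes. In a universal programme with no student exclusion criteria (2.3), students are not selected for high baseline scores, so no mean shift is expected from that source. Season, repeat testing and welfare follow-up remain plausible, though the protocol gives no size for any of them.

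**Conclusion.** The point holds as a conditional one. Fitted as worded, the 3.3 model attributes much of any change common to both arms to YAM, contrary to the comparison set in 1.2. With equal arms, complete data, no YAM effect and an equal shift d at both later surveys, the expected coefficient is 0.50d at zero correlation, about 0.57d to 0.99d over the assumed grid, and 0.91d at ICC 0.02 and r 0.6 (4 x 30). With unequal arms or a shift at one survey the share can be below half, but it is not zero.

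The ICC, r and d are assumptions, and the figures are for the linear model only. The false-positive rates show how sensitive the test would be to a shared shift; they do not show that one will occur. It would go too far to say that the primary analysis is certain to be biased, because an arm-by-occasion model may be what was meant. The wording should be corrected in either case.

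**What to change.** In 3.3, replace the status effect with fixed effects for survey occasion (baseline, immediate post, 3-month) plus a YAM effect at each post-baseline occasion, and test those YAM terms. Keep the random effects for school and participant. Use the same fixed effects in the generalised models for binary and count outcomes.

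The change is one of wording and two occasion terms; it needs no new data and leaves the referral process in 4.3 as it is. If an arm-by-occasion model was always intended, the edit only records it. The cost is the wider standard error: 0.079 to 0.108 SD at ICC 0.02 and r 0.6, and 27-41% over the grid. These figures assume a common baseline mean, which randomisation justifies. Adding a separate baseline arm difference would raise the 0.108 to sqrt(2 x 2 x 0.4/120) = 0.115.

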### 1.4 Trial design

YAM will be evaluated using a randomised waitlist-controlled design. All Education Directorate (government) mainstream secondary schools and all Independent and Catholic schools will be invited to trial YAM through an expression of interest process. The active intervention will take place over a 12-month period, beginning Term 2 2020. Data will be collected via student self-report (Appendix A). Measurement of primary and secondary outcomes will be taken at three time-points: pre-intervention (baseline), immediate post-intervention, and at 3-month follow-up. Parent/guardian consent will be sought for students to participate in the data collection.

**Table 1.** Trial design and data collection timeline

	May-Jul T2	May-Jul T2	May-Jul T2	Aug-Oct T3	Oct-Dec T4
Cluster A schools	Pre-survey	YAM	Immediate post-survey	3-month post-survey	usual classes
Cluster B schools	Pre-survey	usual classes	Immediate post-survey	3-month post-survey	YAM

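### Random effects for school and student, read as intercepts, leave school-level variation in change without an error term, so standard errors will be too small if schools change differently

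*Protocol*

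**What the plan says.** Section 1.5 (Procedure) makes the school the unit of allocation: "Consenting schools will be randomly allocated to the intervention or waitlist arm via cluster randomisation". Section 1.2 sets the primary aim as a "significant decrease in suicidal ideation severity across time", at immediate post-intervention and 3 months relative to baseline, against the waitlist group. Section 1.4 fixes three measurement occasions: "pre-intervention (baseline), immediate post-intervention, and at 3-month follow-up".

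Section 3.3 analyses continuous outcomes by linear mixed models with "fixed effects for intervention status (baseline/unexposed vs post intervention and follow-up occasions") and with "random effects for cluster (school) and for participants within schools". It names no school-by-occasion effect, no random school slope and no basis for degrees of freedom.

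Section 2.7 counts "Government schools: 15 eligible schools and 2378 Year 9 students" and "Non-government schools: 18 eligible schools and 2494 Year 9 students", assumes school participation of 50-65% and student consent of about 20%, and arrives at 119 students per arm. The protocol states no intraclass correlation, standard deviation, alpha, power or target effect.

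**The concern.** A school intercept adds the same amount to a student's score at every occasion. Subtract baseline from follow-up and it is gone. The same holds for the student intercept. With only these two terms, the arm difference in change is judged against within-student residual variance, and nothing in the error reflects schools moving differently from one another.

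The protocol itself describes reasons why they might:

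- **Follow-up of flagged students.** Under Section 4.3, students flagged on ideation or self-harm items are followed up through each school's usual procedures. This happens in both arms, starts at baseline and bears directly on the primary outcome.
- **School-wide events.** Section 2.3 keeps out schools with a recent death or crisis. The same kind of event during follow-up would affect a whole school together.
- **Delivery.** Section 1.5 plans to measure fidelity across schools because it may alter outcomes. This adds variation among YAM schools if the programme has an effect.

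The first two operate even if YAM does nothing. At stake is whether a reported fall in suicidal ideation could be school-to-school noise.

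**Working it through.** **1. The plan's own forecast.** 2378 × 0.5 = 1189 students; 1189 × 0.2 = 237.8; 237.8 / 2 = 118.9, which reproduces 119 per arm. (Section 2.7 prints 19 × 0.5 = 7.5 and 1189 / 0.2 = 238. The stated results follow from 15 × 0.5 and 1189 × 0.2. This does not affect the present point.)

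- Schools: from 15 × 0.5 = 7.5 (government only) to (15 + 18) × 0.65 = 21.45, so about 8 to 21.
- Consenting students per school: 237.8 / 7.5 = 31.7 (government only). With both sectors at 50%, (2378 + 2494) × 0.5 × 0.2 = 487.2 over 33 × 0.5 = 16.5 schools, which is 29.5. About 30 is used below.

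**2. Assumptions, because the protocol gives none.** Total SD 1; school ICC 0.01 to 0.05; school autocorrelation over time (CAC) 0.5 to 1; student correlation 0.6; two-sided alpha 0.05; 4 or 8 schools per arm; complete, balanced data.

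**3. Formula.** Let a = ICC × (1 − CAC) be the school-by-occasion variance, e = (1 − ICC) × (1 − 0.6) the residual variance, m = 30 students per school and k schools per arm. For the arm difference in change between two occasions:

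- true variance = (4/k)(a + e/m)
- variance from the intercept-only model = (4/k)(a + e)/m
- ratio = 1 + (m − 1)ρ, with ρ = a/(a + e)

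The ratio does not contain k, so more schools do not reduce it.

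Worked case, ICC 0.03 and CAC 0.8: a = 0.006, e = 0.388, ρ = 0.006/0.394 = 0.0152. The ratio is 1 + 29 × 0.0152 = 1.44, and the SE ratio is √1.44 = 1.20. With k = 4, the model SE is 0.115 and the true SE 0.138. Type I error = 2[1 − Φ(1.96/1.20)] = 0.103.

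**4. Results over the range** (SE ratio, then type I error from the formula):

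| School ICC | CAC 1 | CAC 0.9 | CAC 0.8 | CAC 0.5 |
|---|---|---|---|---|
| 0.01 | 1.00, 0.050 | 1.04, 0.058 | 1.07, 0.067 | 1.17, 0.093 |
| 0.03 | 1.00, 0.050 | 1.11, 0.076 | 1.20, 0.103 | 1.44, 0.174 |
| 0.05 | 1.00, 0.050 | 1.17, 0.095 | 1.32, 0.138 | 1.67, 0.241 |

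A simulation with 5000 replicates gave 0.06-0.09, 0.10-0.19 and 0.14-0.24 for the three ICCs as CAC falls from 0.8 to 0.5.

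**5. Section 3.3's own coding.** The fixed effect there is coded by exposure rather than as arm by occasion. Repeating the calculation with that coding gives SE ratios of 1.07 to 1.64 for CAC 0.8 to 0.5, so the result does not depend on the coding.

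**6. With a school-level error term.** A t-test on school-level change (6 or 14 df) held simulated type I error at 0.042 to 0.056 throughout. For ICC 0.03 and CAC 0.8, the 95% half-width becomes:

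- 4 schools per arm: from 1.96 × 0.115 = 0.225 SD to 2.447 × 0.138 = 0.34 SD
- 8 schools per arm: from 1.96 × 0.081 = 0.16 SD to 2.145 × 0.097 = 0.21 SD

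**The case against.** The best defence is that Section 3.3 says random effects, not intercepts, and does not say that the two named terms are the only ones. A statistical analysis plan, not shown here, could add a school-by-occasion term and small-sample degrees of freedom. That stands as a limit on certainty: intercepts are the ordinary reading, but still a reading. It does not remove the point, because Section 3.3 does specify the random structure, and the structure it lists omits the term that the primary contrast needs. An analysis plan that follows it inherits the gap.

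A reader might infer that clustering is ignored and the trial is analysed as if students had been randomised. The document does not support that. Section 1.5 recognises cluster randomisation, and the school effect in Section 3.3 covers stable differences between schools. The gap is confined to variation in change.

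A reader might also infer that the standard errors are certainly too small. That does not follow either. With school effects constant over time (CAC 1) there is no understatement, and at ICC 0.01 with CAC 0.8 it is only 7%. The calculation shows what happens if such variation exists; it does not show that it exists in these schools.

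Finally, the simulated control of type I error belongs to the school-level test. The extended mixed model was not simulated, and with 4 schools per arm its school-by-occasion variance would be poorly estimated. This stands and shapes the fix.

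**Conclusion.** The point holds in conditional form. On the ordinary reading of Section 3.3, the model has no school-level error for change from baseline, although schools are randomised. If schools differ in change, the analysis will be anti-conservative for the primary and continuous secondary outcomes, and recruiting more schools will not cure it.

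Across the assumed range the SE is too small by a factor between 1.00 and 1.67, and type I error lies between 5% and about 24%. The upper end needs an ICC of 0.05 with a CAC of 0.5. These figures rest on about 30 students per school, which follows from Section 2.7, and on correlations that the protocol does not give. A student correlation above 0.6 would enlarge the ratios and a lower one would shrink them. No size was computed for the binary and count outcomes.

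**What to change.** In Section 3.3, state school and student random intercepts plus a school-by-occasion random effect. Test the arm-by-occasion contrast with Kenward-Roger or Satterthwaite degrees of freedom that reflect the number of schools.

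Because the added variance is poorly estimated with few schools, also specify a supporting analysis: compare mean school change between arms by a t-test on (schools − 2) degrees of freedom.

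This changes analysis wording only and needs no new data. The price is wider intervals. For the school-level test the critical value is 2.45 with 8 schools and 2.14 with 16, instead of 1.96. The mixed model's approximate degrees of freedom need not equal schools − 2, since they depend on how the school-by-occasion variance is pooled over occasions.

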### 2.4 Intervention

The YAM intervention is a structured program of lectures and interactive role play sessions, consisting of five 1-hour sessions presented over a 3- to 6-week period. More specifically, it consists of one x 1-hour interactive lecture about mental health at the beginning (session 1), three x 1-hour sessions of role-play (sessions 2, 3, 4), and one closing session (session 5). Participants are also provided with a 32-page booklet that reiterates much of the content and includes a localised list of well-being and help-seeking resources. Six educational posters are also displayed in each participating classroom for the duration of the intervention. Content topics are: (1) Awareness about mental health; (2) Self-help advice; (3) Stress and crisis; (4) Depression and suicidal thoughts; (5) Helping a troubled friend; and (6) Getting advice: who to contact.

Nominated YAM instructors attend a 4.5 day training session conducted by YAM certified trainers to be able to deliver the YAM intervention in schools. Participants in the training sessions will take part in role-play sessions to practice how to deliver the intervention, and they will receive feedback from trainers. Upon completion of the course, participants will become certified YAM instructors, and are able to deliver the five session YAM program to adolescents in Australia. YAM instructors can be anyone who has contact with youth, such as psychology and psychiatry professionals, social workers, youth counsellors, social assistants, school guidance counsellors, teachers, school nurses, youth advocates, or support group workers. It is recommended that YAM instructors should not be teachers in the schools in which YAM is being implemented.

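### Read in the ordinary way, the participant random effect in section 3.3 implies equal correlation between all three unequally spaced surveys; if correlation falls with time, the time-specific standard errors are misstated

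*Protocol*

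**What the plan says.** Section 3.3 (Statistical methods) of the protocol sets out the model for the continuous outcomes, which include the primary outcome, suicidal ideation severity: "Linear mixed models will be used to test the effect of the intervention on continuous, scaled outcome measures between groups". Its contents are "fixed effects for intervention status (baseline/unexposed vs post intervention and follow-up occasions") and "random effects for cluster (school) and for participants within schools". The participant effect is the only student-level term. No slope, residual covariance structure or robust variance is named. Other outcome types follow the same pattern: "Binary and count outcomes will be evaluated using generalized extensions of the mixed models used for scaled variables".

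Three surveys are planned: "pre-intervention (baseline), immediate post-intervention, and at 3-month follow-up" (section 1.4). They are unequally spaced. The programme that separates the first two is described in section 2.4 as "consisting of five 1-hour sessions presented over a 3- to 6-week period", and both surveys fall in Term 2. Of Cluster A students, section 1.5 says: "They will then complete a 3-month post survey in Term 3, 2020". The primary aim in section 1.2 is a change "from immediate post-intervention and 3-month follow-up, compared to baseline", relative to the waitlist group.

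**The concern.** A participant random intercept with independent residuals has two variance parameters and one correlation. It treats baseline as equally predictive of a survey a few weeks later and of one about four months later. The ideation items listed in section 4.3 ask about the past two weeks, so a correlation that weakens over the longer gap is a natural expectation, and exact equality is the special case that the model needs.

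If the correlation does weaken, the model estimates one averaged correlation and applies it to both contrasts. The 3-month contrast then looks more precise than it is, and the immediate-post contrast less precise. This arises within students, so it is present even if schools do not differ in change. Missing surveys are affected too. Section 3.3 favours the mixed model because it can keep students with incomplete data, but under data missing at random that property relies on the covariance being correctly specified.

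**Working it through.** **Inputs from the protocol.** The only design figure is 119 students per cluster arm (section 2.7). It is reproduced by 2378 × 0.5 = 1189, 1189 × 0.2 = 237.8, and 237.8 / 2 = 118.9, or 119. (Some operands printed in that section differ; that is a separate matter.) The sample size cancels in the ratios below.

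The gap from baseline to immediate post is 3 to 6 weeks. Adding about 13 weeks puts the last survey at 16 to 19 weeks, about 4 months after baseline.

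**Inputs assumed.** The protocol gives no within-student correlation or variance. I take equal variances, complete data and no school-by-occasion variation. Correlations are listed as baseline-post / post-3-month / baseline-3-month and written r01 / r12 / r02.

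**Formulas.** The true variance of change is proportional to 2(1 − r01) at immediate post and 2(1 − r02) at 3 months. The random-intercept model uses 2(1 − rbar) for both, where rbar is the mean of the three correlations. So:

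- ratio of model SE to true SE = sqrt[(1 − rbar) / (1 − r)], with r = r01 or r02;
- actual two-sided type I error = 2[1 − Φ(1.96 × ratio)].

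**Worked case, 0.70/0.70/0.49.** rbar = 1.89 / 3 = 0.63.

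- 3 months: sqrt(0.37 / 0.51) = 0.852; 1.96 × 0.852 = 1.67; error 9.5%.
- Immediate post: sqrt(0.37 / 0.30) = 1.111; 1.96 × 1.111 = 2.18; error 3.0%.

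A simulation of 20,000 trials with 119 per arm gave 9.4% and 3.0%.

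**Range of patterns.**

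| Assumed correlations | Post: ratio, error | 3 months: ratio, error |
|---|---|---|
| 0.60/0.60/0.60 (equal) | 1.00, 5.0% | 1.00, 5.0% |
| 0.65/0.60/0.55 | 1.07, 3.6% | 0.94, 6.5% |
| 0.65/0.65/0.55 | 1.05, 4.0% | 0.92, 7.0% |
| 0.70/0.60/0.50 | 1.15, 2.4% | 0.89, 8.0% |
| 0.70/0.70/0.49 | 1.11, 3.0% | 0.85, 9.5% |
| 0.55/0.75/0.55 (no decay from baseline) | 0.92, 7.0% | 0.92, 7.0% |

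A steeper case, exponential decay to 0.5 at 18 weeks, gives 0.5% at post and 9.8% at 3 months. Under 0.70/0.60/0.50, several moderate changes in variance across occasions altered the sizes but not the directions.

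**School-by-occasion variation.** I take 0.70/0.60/0.50 with an assumed 4 schools per arm and 30 students per school. A school-by-occasion variance of about 0.5% or 1% of the total gives simulated ratios of 0.94 and 0.84 at post and 0.79 and 0.72 at 3 months. The post standard error is then too small rather than too wide, and the 3-month one smaller still.

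**One pooled effect.** If the two later surveys are averaged into a single contrast, the ratio is 1.00 under 0.65/0.60/0.55 and 0.70/0.60/0.50, 0.92 (error 7.2%) under 0.70/0.70/0.49, and 0.86 (error 9.1%) under 0.55/0.75/0.55.

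**The case against.** The strongest objection is that this is detail for the SAP, which is not shown. Section 3.3 does not say that the participant effect is intercept-only, or that residuals are independent with equal variance. A random slope or a structured residual covariance would be compatible with its wording. That stands against any claim that the protocol forces equal correlation. It does not dispose of the point: the protocol names a dependence structure, and an SAP that implements it in the usual way inherits the equal-correlation assumption.

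A reader might infer that error bars are definitely too small at 3 months and too wide immediately post-intervention. The protocol does not support that. It gives no correlations; equal correlations produce no error; 0.55/0.75/0.55 makes both standard errors too small; and slight school-by-occasion variation can reverse the direction at post. Nor can the immediate-post test be assumed conservative.

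The fixed-effect wording could also mean one pooled status effect, which some decay patterns leave unharmed. That ambiguity is real, but sections 1.2 and 1.3 name both time points, and the pooled contrast is not protected under every pattern.

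Finally, 0.70/0.70/0.49 is what equally spaced first-order autoregression would give, so it fits a complaint about unequal spacing poorly. That is fair. The patterns 0.65/0.60/0.55 and 0.70/0.60/0.50 avoid it and give 6.5% and 8.0% at 3 months.

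**Conclusion.** The point holds conditionally. On the ordinary reading, the stated model implies one common correlation across three unequally spaced surveys. If correlation with baseline falls with time, the time-specific standard errors are misstated. Across the assumed patterns from 0.65/0.60/0.55 to 0.70/0.70/0.49, the error is about 6.5% to 9.5% at 3 months and about 2.4% to 4% at immediate post, instead of 5%.

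This rests on an intercept-only participant effect, independent residuals, separate contrasts at each survey, equal variances, complete data and no school-by-occasion variation. The size is modest under mild decay and nil under equal correlations. Confidence is medium because the true correlations are unknown. The change should still be made: it is nearly free, and settling it before data are seen avoids a data-driven choice.

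**What to change.** For the continuous outcomes, state in section 3.3 that the three surveys per student have an unstructured 3x3 covariance, fitted by REML, in place of the participant random intercept. Keep the school-level terms. Report the arm contrast in change from baseline separately at immediate post and at 3 months.

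Do not name a first-order autoregressive structure as the fallback, even with heterogeneous variances. It gives the short and long gaps the same correlation and sets baseline-3-month to their product. Under equal correlations of 0.6, that product is 0.36, so the 3-month standard error is sqrt(0.64 / 0.40) = 1.27 times too wide (error 1.3%). Under 0.65/0.65/0.55 the fitted ratio is 1.13 (error 2.6%). If a fallback is needed, keep the random intercept with cluster-robust standard errors at school level and a small-sample correction.

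The cost is a sentence or two and four more variance parameters (6 instead of 2), from about 238 students with up to 238 × 3 = 714 records. Little is lost if the correlations are in fact equal. The change repairs the student-level part only; school-by-occasion variation needs its own handling.
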